### 12.3 Statistical Methods

Because this is a pilot study, it is not fully powered to detect differences between groups. Because of emerging consensus that group-to-group comparisons in a pilot study are invalid and misleading, estimating effect size is not one of our study objectives. However, our goal will be to obtain estimates of study parameters to inform power calculations for a subsequent study, including the following:

- Within-group standard deviation of each continuous primary and secondary outcome measure as well as each measure of target engagement; and
- Correlation over time of each outcome measured at baseline and follow-up.

Furthermore, our collection and analysis of process measures will be used to inform changes to the intervention throughout the pilot study in order to optimize its delivery for a future RCT.

## 13 Ethics/Protection of Human Subjects

This study is to be conducted according to applicable US federal regulations and institutional policies (which are based in federal regulations, guidance, and ICH Good Clinical Practice guidelines).

This protocol and any amendments will be submitted to the Boston Medical Center and Boston University Medical Campus IRB, for formal approval of the study conduct. The decision of the IRB concerning the conduct of the study will be made in writing to the investigator. A copy of the initial IRB approval letter will be provided to the sponsor before commencement of this study.

All subjects for this study will be provided a consent form describing this study and providing sufficient information for subjects to make an informed decision about their participation in this study. The consent form will be submitted with the protocol for review and approval by the IRB. The consent of a subject, using the IRB-approved consent form, must be obtained before that subject is submitted to any study procedure. Consent will be documented as required by the IRB.

## 15 Appendix

### Schedule of Events

Domain/measure	Informant	Assessment Time Point (Month)			Intervention Period (0-3+ months)
		0	3 (Post-intervention)	6	
Family Background					
Background Socio-demographic Questionnaire	Parent	X			
Unmet Social Needs Questionnaire and Adequacy of Resources	Parent	X	X	X	X
Child Symptoms, Adverse Experiences, and Treatment Utilization					
Child Behavior Checklist 1.5-5	Parent	X		X	X
ADHD Rating Scale, Version IV (ADHD-RS-IV), Preschool Version	Parent	X	X	X	X
CYW Adverse Childhood Experiences Questionnaire (ACE-Q) Child	Parent	X			X
Parent Symptoms, Activation and Treatment Utilization					
Patient Health Questionnaire (PHQ-9)	Parent	X	X	X	X

Adult ADHD Self Report Scale (ASRS-v1.1)	Parent	X	X	X	X
Perceived Stress Scale (PSS)	Parent	X	X	X	X
Parenting Stress Index-Short Form (PSI-SF)	Parent	X	X	X	X
Intervention Feasibility, Acceptability, and Content					
PRE-CARE Exit Interview – PRE-CARE condition only	IE (via Parent)		X		
PRE-CARE Feasibility and Acceptability Form - PRE-CARE condition only	Parent		X		
Interventionist Post-Session Summary Form - PRE-CARE condition only	RA	X	X		
Premature Termination Form	RA	X	X

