***Intervention Part 3, Resource Navigation.*** Interventionists will discuss further with families the details of specific needs indicated during screening in order to best tailor assistance provided. Based on this conversation, the interventionist may offer more intensive support navigating to certain resources for families where it is needed. Interventionists will have a companion Navigation Resource Booklet that includes workflows and algorithms to assist with referral decisions for families. The level of interventionist involvement will be based on the family's particular needs, community resources available, and a shared decision-making process between the interventionist and family. For example, some participating parents may choose to

simply contact agencies listed in the Family Resource Booklet on their own, and not request any further support from the interventionist. Other families may want more assistance contacting and accessing community resources. In these cases, the interventionist may place referrals, coordinate services, or contact community agencies and providers on behalf of the family to inquire about resources.

As a default, the interventionist will offer follow-up meetings with the participating caregiver (either in-person, by phone, or via videoconference) every two weeks until three months have passed since the randomization date. The interventionist may end the intervention period later for the participant whose needs require longer than three months to resolve. The interventionist may also end the intervention period earlier than three months for the participant if all needs mentioned by the participant have been resolved. All forms of interventionist contacts (in-person appointments, emails, phone, and text message exchanges) and community resources placed on behalf of participating families will be documented in the participant's electronic medical record and logged by the interventionist in the study record. Interventionists will also log the length of time per contact. At each contact, interventionists will also inquire about resources received since last contact, and about whether additional help is needed for that need, or other (even new) needs. They will also ask for feedback about resources received and our process for helping families. Contacts will vary in time length (e.g., 5-10 minute calls vs. 1 hour long meetings) depending on the needs of each family.

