### **Randomization Procedures**

Once a caregiver gives consent to enroll in the study, they will be provided with a unique ID number and this ID number will be connected to their identifiable data (access to identifiable data will be limited to only research staff members and investigators listed on the IRB). Once consent and baseline assessment are completed, the caregiver/family will be randomized. Participants will be randomized to either the PRE-CARE intervention or to the care as usual control condition through the computerized randomization feature of REDCap. If a participating caregiver has multiple eligible children, they will be randomized by family. Randomization will be stratified by primary language (English and Spanish). Due to the nature of the intervention, we will not be able to blind study participants or research assistants serving as interventionists. Study assessments will be completed by parents independently, but if assistance is needed, it will be provided by a separate research staff member who is not the interventionist.

After the random assignment has been generated in REDCap, research staff will contact participants by phone to share their assignment, and with their permission, also inform the clinical care team of the study assignment. If a participant is randomized to the PRE-CARE intervention, research staff will then schedule their first study visit with the family. Research staff will aim to schedule this first study visit as soon as possible, preferably within one week of the date that the random assignment was generated. If a participant is randomized to care as usual, the parent will be advised to follow up with their clinical providers to determine the next steps for their child's treatment according to the standard of care at their clinical site. Clinical providers will also be advised that the family has been randomized to care as usual. Results of psychometric tools (i.e., CBCL 1.5-5 and ADHD-RS-IV-Preschool Version) will be shared with providers for all families with permission of the participating parent. Research staff will not contact the families in the control condition again until the time of follow-up assessments at 3, 6, and 12 months following completion of baseline assessments.

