### Parent-Reported Study Assessments

In addition to the baseline assessments, all 60 participants (30 intervention and 30 control) will complete follow-up assessments at 3, 6, and 12 months following the completion of baseline assessments. Follow-up assessments can be completed in person at the research office, in the participant's home, or remotely by phone or videoconference.

Participants in the intervention arm only will also be invited to participate in an in-depth exit interview once their intervention period is complete in order to collect feedback on the intervention content and strategy and explore putative intervention mechanisms. If participants refuse to participate in the exit interview, but complete the survey assessments, they will still be compensated.

At any of the assessment timepoints, if participants refuse to complete select questions in the assessments, but answer most questions, they will still be compensated.

It is anticipated that in some cases, two primary caregivers will desire to be part of the intervention. Other adult family members involved in primary caregiving may also participate in any intervention sessions as long as the consenting primary caregiver is present for all sessions and is the only one completing all intervention assessments.

At baseline, participants will complete a Contact Information form that details their preferred mode of contact for completion of follow-up assessment (email, phone, mail). At each subsequent time point, RAs will refer to the contact information form and send reminders (via email, phone, or text message, based on preference) to the participant to complete their follow-up assessments every 4 days for at least 2 weeks (or until the assessment is complete). RAs will run weekly reports off REDCap to see which participants have not completed their assessments. If a participant has not completed their assessment after 2 weeks, the RA will call the participant to complete the assessment over the phone. At each of the follow-up timepoints (3, 6, and 12-months after baseline), RAs should stop reminder calls to participants 8 weeks after the participant was initially contacted to complete the assessment.

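### For families whose intervention is extended, or who are randomized some days after baseline, the month-3 assessment labelled post-intervention falls due before the intervention ends, and the acceptability form is timed to it

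*Combined protocol and SAP*

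**What the plan says.** **Follow-up clock.** Section 9 (Parent-Reported Study Assessments) says that all participants "will complete follow-up assessments at 3, 6, and 12 months following the completion of baseline assessments". Section 9 (Randomization Procedures) repeats this anchor for control families, who are not contacted again "until the time of follow-up assessments at 3, 6, and 12 months following completion of baseline assessments".

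**Intervention clock.** Under Randomization Procedures, "Once consent and baseline assessment are completed, the caregiver/family will be randomized". No limit is set on the gap between the two. The first intervention visit is aimed for "preferably within one week of the date that the random assignment was generated". In Section 8 (Resource Navigation), meetings are offered "every two weeks until three months have passed since the randomization date".

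**Variable length.** Section 8 adds: "The interventionist may end the intervention period later for the participant whose needs require longer than three months to resolve". Section 5 also allows extension, and neither section states a ceiling. Both let the intervention end early once needs are resolved. The list of ending conditions at the start of Section 8 includes the passing of three months and a family's request to stop. It does not mention extension.

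**Schedule.** Section 15 labels month 3 "3 (Post-intervention", while its intervention-period column is headed 0-3+ months. The exit interview and the Feasibility and Acceptability Form, both for the PRE-CARE arm only, are marked at month 3. Section 9, however, invites intervention participants to an in-depth "exit interview once their intervention period is complete". The schedule is the only place that times the form.

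**The concern.** The label month 3 carries in the schedule is true only if the intervention has ended by then. Two features work against that: the assessment clock starts no later than the intervention clock, and the intervention can be extended with no stated limit. A column headed 0-3+ months beside a month-3 column called post-intervention cannot be right for an extended family.

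Three things are at stake.

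- **Acceptability ratings.** Optimizing delivery is a main objective (Section 4.1), and the feasibility and acceptability questionnaire is a listed outcome (Section 4.2.1). A form filled in mid-course misses the rest of the intervention.
- **Selection.** Extension is for families whose needs take longer to resolve, and unmet social needs is a proposed measure of target engagement. Being on or off the intervention at month 3 is therefore tied to something being measured.
- **Planning parameters.** Section 12.3 will supply within-group SDs and baseline-to-follow-up correlations for the next trial. At month 3 these would mix families on and off the intervention under one label.

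**Working it through.** The plan states no figure to reproduce. This is date arithmetic, with three months taken as 91 days (365.25 / 4, rounded).

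**Inputs from the plan**
- Month-3 due date: day 91 from baseline completion (Section 9).
- Default intervention end: 91 days after randomization (Section 8).
- Reminders stop 8 weeks (56 days) after first contact for a time point (Section 9).

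**Assumed inputs, because the plan gives none**
- L, days from baseline completion to randomization: 0 to 28.
- E, days of extension (positive) or early finish (negative): -42 to +91.

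**Formulas**
- Intervention end = L + 91 + E.
- Due date minus end = 91 - (L + 91 + E) = -(L + E).

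Days from intervention end to the month-3 due date (negative means that the assessment comes first):

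| L | E = -42 | E = -14 | E = 0 | E = 28 | E = 56 | E = 91 |
|---|---|---|---|---|---|---|
| 0 | +42 | +14 | 0 | -28 | -56 | -91 |
| 7 | +35 | +7 | -7 | -35 | -63 | -98 |
| 14 | +28 | 0 | -14 | -42 | -70 | -105 |
| 28 | +14 | -14 | -28 | -56 | -84 | -119 |

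**Reading the table**
- Default length (E = 0): the gap equals the lag, and is zero if the family is randomized on the day baseline is completed.
- Extended: the assessment always comes first, because L is at least 0 and E is above 0. With L = 0 and E = 91 the intervention ends on day 182, when the month-6 assessment falls due (2 x 91 = 182).
- Early finish: the assessment comes after the end whenever the days saved exceed the lag.

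**Late completion.** If first contact is on the due date and the form is completed at the 8-week limit, it is done on day 91 + 56 = 147, which is 56 - (L + E) days after the end. It falls on or after the end when L + E is 56 or less. For L = 0 and E = 91 it is still 35 days before the end (56 - 91 = -35).

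**Re-anchoring.** If follow-up were counted from randomization, the due date would be L + 91 and the gap would be -E. The lag disappears, but the extension gap is unchanged.

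**The case against.** The strongest reply is that this is mostly a label, and that the plan already handles the rest.

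- **Exit interview.** Section 9 already ties it to the end of the intervention. This stands: staff who follow that text would not interview an extended family mid-course. The schedule still says otherwise, and nothing in the text does the same for the form.
- **Damaged table.** In the text available, the schedule has lost its month-12 heading, so single marks are weak evidence of column position. The placement of the form's mark should be checked against the source file. The month-3 label and the 0-3+ heading are legible and conflict without it.
- **Baseline anchor.** A fixed interval from baseline suits a baseline-to-follow-up correlation. This stands, and is why the fix does not depend on moving the anchor.
- **Recoverable status.** Section 9 (Research Staff-collected Process Outcomes) records contact dates, need-resolution dates and intervention dropout. On or off status could often be rebuilt from these, although no intervention end date is listed. An acceptability rating taken at the wrong time cannot be rebuilt.

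A reader might also infer that month 3 precedes the intervention end in every family, or in every full-course family. The documents do not support that. Same-day randomization with the default length gives a gap of zero, early finishers are assessed afterwards, and the 8-week window can move completion past the end. Nor do they support an inference of between-arm bias: both arms share the baseline clock, and Sections 12.2 and 12.3 say that effect size will not be estimated.

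**Conclusion.** The point holds for two groups. For extended families, the month-3 due date falls before the intervention ends by at least the length of the extension. For full-course families randomized some days after baseline, it falls before the end by that lag. The lag is probably small, since randomization follows directly on baseline completion; extension is what matters.

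The sizes (7 to 28 days from lag alone, 28 to 91 days from extension alone) rest on assumed values. The number of families affected cannot be derived, because no extension rate or lag is given.

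If the schedule is followed as written, extended families complete the acceptability form mid-course, and the exit interview's placement contradicts Section 9. The month-3 SDs and correlations would describe a mix of families on and off the intervention. This is a cheap improvement to data collection for a main objective of the pilot, not a threat to a treatment comparison.

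**What to change.** 1. Reconcile Section 5, the list of ending conditions and the Resource Navigation text in Section 8, Parent-Reported Study Assessments in Section 9, and the Schedule of Events, so that the length of the intervention and the timing of its closing measures read the same throughout.
2. Relabel the month-3 column by its actual anchor: 3 months after baseline.
3. Give the Feasibility and Acceptability Form, like the exit interview, at each family's intervention end, and show both that way in the schedule.
4. Add an intervention end date to the study record. Use it to flag month-3 data, or to summarise month-3 SDs and correlations, by on- or off-intervention status.

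Counting follow-up from randomization is optional. It removes the lag but leaves extended families on the intervention at month 3.

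**Cost.** Wording, one date field and a changed trigger for the form, with no added study visits. The downside is that the form is no longer completed at a single fixed time point, so its timing must be reported alongside the ratings.
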